### 12.3 Procedures and Time Period for Detecting Adverse Events

The Investigator or designee is responsible for detection, recording and reporting of events that meet the criteria and definition of AEs.

As a consistent method of soliciting AEs, the participant shall be asked a nonleading question such as: "How do you feel?".

The presence or absence following 'solicited AEs' will be assessed by direct questioning:

- stuffy nose
- runny nose
- sneezing
- nasal irritation
- nasal tenderness/ pain
- loss of smell
- sore throat/ scratchy throat
- cough

Detection and recording of study related AEs and SAEs extends from the signing of the consent form until completion of the last study related procedure (including follow-up for safety assessments). Any AE reported or observed at or after the start of dosing with study drug will be recorded as a treatment-emergent AE (TEAE) or SAE.

Any pre-existing conditions or signs and/or symptoms present in a participant prior to the start of the study (i.e., before informed consent), should be recorded as medical history. In addition, any change in health status that is reported or observed after informed consent but prior to starting study drug and is deemed by the study Investigator to be "not related" to study procedures, will be documented as medical history.

A post-study AE/SAE is defined as any event that occurs outside of the nominal AE/SAE study detection period. Investigators are not obligated to actively seek AEs/SAEs in former study participants. However, if the Investigator learns of any SAE, including a death, at any time after a participant has completed the study and he/she considers the event reasonably related to the investigational product, the Investigator will promptly notify the Sponsor.

Participants must be provided with an “Emergency Wallet Card” indicating the name of the investigational product, the study number, the Investigator’s name, a 24-hour emergency contact number, and, if applicable, excluded concomitant medications.

#### **12.4 Recording of Adverse Events and Serious Adverse Events**

All AEs, regardless of seriousness, severity, or presumed relationship to study drug, must be recorded in the eCRF using medical terminology in the eCRF and/or other sources. Whenever possible, diagnoses should be given when signs and symptoms are due to a common etiology (e.g., cough, runny nose, sneezing, sore throat, and head congestion may be reported as “upper respiratory infection”). Investigators must record in the eCRF the date of onset of the event, their opinion concerning the relationship of the event to study drug, severity of the event, whether the event is serious or nonserious, actions taken to manage the event, the outcome of the event, and date of resolution where applicable.

Any change to the severity of an AE must be recorded as a separate AE, ensuring that the end date and time of the preceding AE matches the start date and time of the subsequent AE, so that the overall duration of the AE is continuous.

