2.2 Objectives

2.2.1 Primary Objectives and Endpoints

The primary objective of this study is:

- To determine the safety and tolerability of single and multiple doses of intranasally delivered LMN-301.

The primary endpoints of this study are:

- The occurrence of solicited AEs for 28 days after the first dose of LMN-301.
- The occurrence of unsolicited AE/SAEs for up to 28 days after the first dose of LMN-301.
- Discontinuation.
- Changes from baseline in vital signs, safety laboratory parameters, ECG parameters and nasal symptoms using the Sino-nasal outcome test (SNOT-22).

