13.1 Adverse Events

AE verbatim terms will be coded using the version 25.1 of the Medical Dictionary for Regulatory Activities (MedDRA). AEs and SAEs are defined in the study protocol.

- Treatment Emergent Adverse Events (TEAEs) are defined as adverse events that occurred or worsened from the first administration of study drug. If determination cannot be made as to whether the event is treatment emergent due to missing or incomplete data, the adverse event will be treated as treatment emergent.
- Treatment-Related AEs are defined as any TEAEs reported with the causality of “Related” to study treatment.
- Solicited AEs will be assessed by direct questioning and include stuffy nose, runny nose, sneezing, nasal irritation, nasal tenderness/pain, loss of smell, sore/scratchy throat, and cough.
- Unsolicited AEs include all other AEs not classified as Solicited adverse events.

All AE summaries will be restricted to TEAEs only.

The TEAE summaries will include:

- Overall Summary of TEAEs
 - TEAEs
 - TEAEs by Severity (Grade 1 to Grade 5)
 - TEAEs by Relationship
 - Treatment Related TEAEs
 - Serious TEAEs
 - Treatment Related Serious TEAEs
 - Solicited TEAEs
 - Unsolicited TEAEs
 - TEAEs leading to Death
 - TEAEs leading to Study Withdrawal

The following table summaries will be presented by SOC and PT by treatment groups defined in Section 4.6:

- TEAE summary by SOC and PT
- TEAE summary by SOC, PT and Severity
- TEAE summary by SOC, PT and Relationship
- Treatment Related TEAE summary by SOC and PT
- Treatment Related TEAE summary by SOC, PT and Severity

- Serious TEAE summary by SOC and PT
- Treatment Related Serious TEAEs summary by SOC and PT
- Solicited TEAE summary by SOC and PT
- Unsolicited TEAE summary by SOC and PT

The above items will be presented using summary tables, which will include the number of participants (%) experiencing an event and the number of events. If a participant experienced the same adverse event multiple times, this will only be counted once for the purpose of counting the number of participants experiencing that adverse event. Summary tables will be done for the SS population for treatment groups defined in Section 4.6. Where SOC and PT are reported, the display will be sorted by the descending order of occurrences of SOC and PT, followed by alphabetical sorting. In Part B, summaries will be sorted based on counts in the overall treatment group.

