All AEs will be listed and will include the verbatim term, SOC, PT, SAE, start/end date/time, causality/severity, relationship to study treatment, outcome, action taken, solicited [yes/no] and study withdrawal. A separate listing will be created for SAEs, those leading to Death, and those leading to Study Withdrawal. These listings will be presented by treatment groups defined in section 4.6, sorted by participant ID and AE start date for the SS population, along with age, sex, race, and baseline weight of the participant.

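### The diagnosis-for-symptoms rule in Protocol 12.4 can move up to four of the eight solicited AEs into one unsolicited diagnosis, and so can undercount a primary endpoint

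*Protocol*

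**What the plan says.** - **Collection.** Protocol 12.3 names eight symptoms and specifies: "The presence or absence following 'solicited AEs' will be assessed by direct questioning". SAP 13.1 agrees: "Solicited AEs will be assessed by direct questioning and include stuffy nose, runny nose, sneezing, nasal irritation", and its list continues with nasal tenderness or pain, loss of smell, sore or scratchy throat, and cough.
- **Recording.** Protocol 12.4 says: "Whenever possible, diagnoses should be given when signs and symptoms are due to a common etiology". In its example, "cough, runny nose, sneezing, sore throat, and head congestion may be reported as" an upper respiratory infection.
- **Classification.** SAP 13.1: "Unsolicited AEs include all other AEs not classified as Solicited adverse events".
- **Endpoint.** SAP 2.2.1 lists as primary: "The occurrence of solicited AEs for 28 days after the first dose of LMN-301". Protocol Table 5-A has the same endpoint. Neither makes it depend on cause.
- **Reporting.** SAP 13.1 plans a "Solicited TEAE summary by SOC and PT". Its AE listing carries "outcome, action taken, solicited [yes/no] and study withdrawal". No rule is given for setting the solicited item on a record that holds a diagnosis.

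**The concern.** Two instructions do not fit together. One asks about each symptom separately. The other encourages the investigator to replace a group of symptoms with one term, and its example is built largely from the symptoms being asked about.

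The overlap includes effects that the sponsor expects. Protocol 4.3 anticipates sneezing, nasal discharge, nasal tenderness or pain, and nasal irritation after dosing, and the first two of these also appear in the 12.4 example. Whether such a cluster is a reaction to the powder or a cold is left to an unblinded investigator in a study without a control group. The schedules include a COVID-19 rapid antigen test but no test for other respiratory viruses, so a cold is a clinical judgement.

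At stake is the count behind a primary endpoint in groups of 10, and the symptom-level profile of an intranasal product.

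**Working it through.** **1. The plan's own figures.** The only design figures are the chances of seeing at least one SAE at a true rate of 10% (Protocol 13.1, SAP 3). They reproduce: 1 − 0.9^35 = 97.50% (stated as over 97%) and 1 − 0.9^30 = 95.76% (stated as over 95%). This point does not affect them. The documents give no figure for solicited events.

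**2. Overlap of the two lists.**
- Solicited (8): stuffy nose, runny nose, sneezing, nasal irritation, nasal tenderness/pain, loss of smell, sore/scratchy throat, cough.
- Example in 12.4 (5): cough, runny nose, sneezing, sore throat, head congestion.
- In both: cough, runny nose, sneezing, sore throat = 4 of 8. Head congestion is not a listed term. It may overlap with stuffy nose, so five is arguable, but four is the firm count.

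**3. One cluster of these four symptoms followed through the plan.**
- Symptoms recorded separately: 4 solicited events, and the participant is counted.
- Diagnosis only, solicited item set to no: 0 solicited events and 1 unsolicited event.
- Diagnosis only, solicited item set to yes: the participant is counted, but the table by preferred term shows 1 diagnosis in place of 4 symptoms.

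The documents do not choose between these. Compared with separate recording, merging can lower the solicited event count (4 to 1, or 4 to 0) and cannot raise it. A merged record also takes a single severity grade, that of its worst aspect (Protocol 12.2.1).

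**4. Effect on incidence.** Each Part B group has 10 participants (Protocol 6.3). One participant leaving the solicited numerator changes the group's incidence by 1/10 = 10 percentage points and the Part B overall figure by 1/30 = 3.3 points. This needs the second recording route in step 3 and no other solicited event recorded for that participant during follow-up.

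**5. How often.** The documents do not say. As an illustration only, let u be the share of participants with a cold-like illness and q the share of those recorded as an unsolicited diagnosis alone. The expected number losing these symptoms from the solicited table is n × u × q. Both ranges, u = 5–20% and q = 25–100%, are assumptions.
- Group of 10: from 10 × 0.05 × 0.25 = 0.1 to 10 × 0.20 × 1 = 2.0.
- All 35: from 35 × 0.05 × 0.25 = 0.4 to 35 × 0.20 × 1 = 7.0.

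The number leaving the incidence numerator would be the same or smaller, because some of these participants would have another solicited event recorded. If symptoms are always kept as separate records, q = 0 and the loss is 0.

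**6. Other places that might recover the symptoms.** The diary records solicited events (Protocol 11.16), but the SAP plans no diary-based summary. SNOT-22 uses a two-week recall and only its total score is summarised, with individual symptoms listed (SAP 13.7). Neither restores the solicited count.

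**The case against.** A reader might infer that the rule does convert these symptoms and that the endpoint is undercounted. The documents do not support that. The rule applies only when the investigator judges that the symptoms share a cause, and its example is permissive. Nothing forbids recording the symptoms as well. An isolated sneeze or runny nose after dosing remains a solicited event.

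A reader might also infer that the SAP sends every term outside the list of eight to the unsolicited table. It does not say so. It describes solicited events by how they are assessed as well as by list, it defines unsolicited events as those not classified as solicited, and it carries the solicited item as a separate field. That field could be set to yes on a diagnosis. The eCRF is not among the documents, so a dedicated symptom form may exist.

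A third inference would be that the study's overall picture of local tolerability is biased in the product's favour. That goes too far. A diagnosed event still appears in the all-TEAE, severity, relationship and unsolicited tables. Change in SNOT-22 is itself a primary endpoint, and rhinoscopy findings are recorded as AEs (Protocol 11.12). The safety analyses are descriptive, and the stopping rules in Protocol 6.4.2 do not use solicited incidence.

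These points limit how certain and how large any loss is. They do not remove the conflict: no text exempts solicited symptoms, no text says how the field is set, and an event kept in another table does not restore the solicited-event endpoint.

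**Conclusion.** The point holds as a possibility written into the plan. If Protocol 12.4 is followed as worded, up to four solicited symptoms can become one unsolicited diagnosis, and the solicited-event primary endpoint can be undercounted. Any error in that count is downward. The worst case for one participant is 10 percentage points in a Part B group of 10, provided that the diagnosis is classified as unsolicited and no other solicited event is recorded for that participant. The frequency is unknown, and the range in step 5 rests on assumed rates. Sample size and SAE detection probabilities do not change. This is more than missing detail, because the protocol's own example cuts across its symptom-by-symptom collection and no planned summary recovers the counts. It should be corrected.

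**What to change.** **Protocol 12.4 or the CRF completion guideline:** state that the eight solicited AEs are always recorded individually, and that a diagnosis may be recorded in addition and linked to them.

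**SAP 13.1:** derive the solicited flag and the solicited table from the symptom-level answers (direct questioning or diary, where captured at that level). State that a linked diagnosis is not double counted in the overall TEAE total.

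SAP 16 describes all enrolled subjects as having received at least one dose, so collection may already be advanced. The SAP sentence may then be the more practical route, but it works only if symptom-level answers are in the database, which the documents do not confirm.

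**Cost:** one sentence in the protocol or guideline, a short addition to the SAP, and slightly more AE records. The solicited count will also include symptoms of intercurrent colds. That fits an endpoint defined regardless of cause, and the linked diagnosis and relationship assessment will identify them. No sample size or study procedure changes.

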#### *13.7.1 Adverse Event Data*

All AEs will be coded using the latest version of MedDRA by SOC and preferred term, classified from verbatim terms. The number of treatment-emergent AEs (TEAEs) as well as the number and percentage of participants with at least one TEAE, will be summarised by SOC and preferred term. Summaries of TEAEs by severity and relationship will also be presented. Summaries will also be presented for SAEs, TEAEs leading to death or study withdrawal. The duration of all AEs will be determined and included in the listings.

Solicited and unsolicited TEAEs will also be summarised separately. Further details will be provided in the SAP.

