$$(\text{Actual PK Sample Collection Time Post Dose}) - (\text{Scheduled PK Sample Collection Time Post Dose})$$
- AE Duration: Adverse event duration (in days, to two decimal places), calculated as

$$(\text{Resolution Date} + \text{Resolution Time}) - (\text{Onset Date} + \text{Onset Time})$$

AE duration will only be calculated for events with complete dates/times and will be undefined for events that are 'Ongoing' at the end of the study.
- Any quantitative laboratory parameters that are given as '<xx' or '>xx' in the database will be imputed with the absolute value of the number without the sign (e.g., <2.2 will be imputed as 2.2) for the calculation of the changes from baseline and for the descriptive statistics. In the listings, no imputations will be performed, and all data will be displayed as recorded in the database.
- Laboratory Parameters:

The L/N/H indicator will be derived, where both the lower and upper limit of the reference range was provided, by following derivation:

 - If the result is less than the lower limit of the reference range, the indicator will be set as "Low".
 - If the result is greater than the upper limit of the reference range, the indicator will be set as "High".
 - If the result is greater or equal to the lower limit of the reference range and less or equal to the upper limit of the reference range, the indicator will be set as "Normal".

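### Each severity change is recorded as a separate AE and the SAP has no rule to rejoin the records, so the event column can be inflated and a participant can fall under two grades; participant percentages are safe

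*Protocol*

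**What the plan says.** **Recording.** Protocol 12.4 (Recording of Adverse Events and Serious Adverse Events) requires: "Any change to the severity of an AE must be recorded as a separate AE". It applies to changes in either direction. The sentence goes on to require sites to join the records in time, "ensuring that the end date and time of the preceding AE matches the start date and time of the subsequent AE", and gives the reason: "so that the overall duration of the AE is continuous".

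**Counting.** Protocol 13.7.1 (Adverse Event Data) asks for two quantities: "The number of treatment-emergent AEs (TEAEs) as well as the number and percentage of participants with at least one TEAE". SAP 13.1 (Adverse Events) repeats this for its summary tables, "which will include the number of participants (%) experiencing an event and the number of events". For a participant who has the same AE more than once, the SAP says "this will only be counted once for the purpose of counting the number of participants experiencing that adverse event". It gives no corresponding rule for the event count.

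**Severity.** SAP 13.1 plans TEAE tables by SOC, preferred term and severity, and severity rows (Grades 1 to 5) in the overall summary. It does not say that a participant is placed at the highest grade.

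**Duration.** SAP 4.3 (Key Definitions) defines "Adverse event duration (in days, to two decimal places), calculated as" resolution date and time minus onset date and time. Protocol 13.7.1 says where it goes: "The duration of all AEs will be determined and included in the listings".

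**The concern.** The recording rule deliberately divides one reaction into consecutive records, one per severity level, while making clear that they belong together. The analysis rules never put them back together. A participant whose nasal irritation goes from mild to moderate and back to mild has had one reaction, but the database holds three AEs.

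Two outputs are exposed. The first is the event column in the AE tables, including the solicited TEAE table. The second is the set of by-severity summaries, where that participant can be counted under both Grade 1 and Grade 2 for the same preferred term, or a programmer has to choose a convention the SAP does not give. With 10 participants per Part B group, a few fluctuating reactions would visibly change the event column, and a reader of the report could not tell repeated reactions from one reaction that changed grade.

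**Working it through.** **Inputs.** The recording, counting and duration rules are those set out above. The documents give no expected AE rate and no expected number of severity changes, so there is no figure of the plan's own to reproduce on this point. The only design calculation (Protocol 13.1, SAP 3) concerns SAEs at a 10% rate: 1 − 0.9^35 = 97.5% and 1 − 0.9^30 = 95.8%. These agree with the stated figures of over 97% and over 95%, and have no part in what follows.

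**Step 1: one AE.** An AE with k severity changes has k + 1 severity segments and so k + 1 records. The counted-once rule reduces the participant count to 1. Nothing reduces the event count, which is k + 1.

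**Step 2: a worked group (assumed data).** Take a group of 10 in which 4 participants each have one 5-day reaction going Grade 1, Grade 2, Grade 1, so k = 2.

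| | As written | Records linked |
|---|---|---|
| Participants | 4/10 = 40.0% | 4/10 = 40.0% |
| Events | 4 × 3 = 12 | 4 |
| Mean listed duration | 5/3 = 1.67 days | 5.00 days |
| Participants under Grade 1 / Grade 2, if no maximum-grade rule is applied | 4 / 4 | 0 / 4 |

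For k = 0, 1, 2, 3, 4 the event count as written is 4 × (k + 1) = 4, 8, 12, 16, 20. It is 4 throughout once records are linked.

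**Step 3: the whole column.** Suppose N AEs occur and a share f of them have k changes each. The reported total is N(1 − f) + N×f×(k + 1) = N(1 + f×k), so the multiplier is 1 + f×k. All values of f and k here are assumptions.

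| | k = 1 | k = 2 | k = 3 |
|---|---|---|---|
| f = 10% | 1.10 | 1.20 | 1.30 |
| f = 25% | 1.25 | 1.50 | 1.75 |
| f = 50% | 1.50 | 2.00 | 2.50 |

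**Step 4: duration.** The end of each segment is the start of the next, so the segment lengths add back exactly: (t1 − t0) + (t2 − t1) + (t3 − t2) = t3 − t0. The full duration can be recovered from the data the protocol requires. The SAP formula applied record by record does not recover it.

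**The case against.** Several points against the concern stand.

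- **Event is not defined.** The SAP never says what its event column counts, so counting records is an inference. It is the natural one, because the protocol calls each segment a separate AE and no collapsing rule exists. If the sponsor intends something else, the SAP still has to say so.
- **The main safety result is protected.** A reader might infer that the solicited-AE primary endpoint is itself inflated. The endpoint is the occurrence of AEs, which reads naturally as participants affected, and the counted-once rule keeps that number and its percentage correct in the SOC/PT tables.
- **Duration.** A reader might infer that the study will report understated durations. No duration summary is planned. Duration is for listings, which carry start and end date and time and are sorted by participant and AE start date, so the segments can be seen and joined.
- **Dosing groups.** A reader might infer that daily dosing (12 doses, against 4 and 6) inflates counts most in Group 3. More doses may bring more grade changes, but daily dosing could also hold a reaction at one steady grade. Reactions that resolve between doses are separate AEs whatever 12.4 says. The documents do not settle the direction, and SAP 13.1 plans no formal AE comparison between groups.
- **Frequency of grade changes.** The documents do not say that participants grade severity daily in the diary. Direct questioning covers whether each solicited symptom is present (Protocol 12.3), and the Investigator assigns CTCAE grades (Protocol 12.2.1). Fluctuation within Grade 1 creates no new record, so f may be small.

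These points limit the consequence. They leave the event column and the by-severity tables without a rule.

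**Conclusion.** The concern holds for two outputs. As written, the event column counts an AE with k severity changes k + 1 times, and the by-severity summaries can show one participant under more than one grade for the same preferred term. Under the assumed values above, the event total is multiplied by 1.10 to 2.50; the true factor cannot be derived from the documents and is 1 if no AE changes grade. The conclusion rests on reading each record as an event, which follows from the recording rule and the lack of a collapsing rule but is not stated outright.

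It does not extend to participant counts and percentages in the SOC/PT tables, to any summary of duration, or to a claim that one dosing group is favoured. In a descriptive Phase 1 study this is a modest defect, worth correcting because the remedy is cheap and already supported by the data structure.

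**What to change.** Leave the recording rule in Protocol 12.4 as it is and amend the SAP.

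- **SAP 13.1, event counts:** treat records of the same AE in one participant as one event when the end date and time of one equals the start date and time of the next, and assign that event its maximum severity.
- **SAP 13.1, by-severity tables:** count each participant once, at the maximum grade, within each SOC and preferred term.
- **SAP 4.3, duration:** calculate from the first onset to the final resolution of the linked records.
- **Listings:** keep the split records so that the course of severity remains visible.
- **Partial times:** SAP 4.3 anticipates incomplete dates and times, where exact matching fails. Review those records manually before the counts are final.

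The cost is one derivation, a few lines of SAP text and a small manual check. No new data are needed, because the protocol already requires the times to match. If the database is already locked, SAP 1 provides for describing the change and its reason in the CSR.
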